## **8.5 The patient is scheduled for surgery (standard of care)**

## **8.6 Presentation of data to the primary surgeon (research)**

Antibiotics are standard of care prior to urologic stone surgery, yet generic recommendations allow for variable prescribing practices. In order to provide precise, individualized prophylaxis antibiotics, we will provide the primary surgery and prescriber the following information without mandating a specific antibiotic:

1. Standard of care urine culture.
2. Next-generation sequencing report – contains bacteria presence and resistance gene profiles.
3. Infectious disease pharmacist first and second choice antibiotics based on NGS report.
4. When NGS report and ID pharmacist recommendations are provided, enrolled provider-participants will be asked to complete a survey (research only) regarding their antibiotic selection with rationale.

## **8.7 Follow-up phone call contact (research)**

The study staff will conduct a chart review and/or telephone follow up approximately 7-14 days post urologic procedure to assess for complications, infections related to the procedure, and antibiotics prescribed. In the event an infection or complication related to the procedure is identified by study staff before patient's clinical follow up visit, study staff will alert medical team and provider if patient has not done so.

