## 1.0 STUDY SYNOPSIS

This is a randomized controlled clinical study evaluating the use of next-generation sequencing (NGS) to improve antibiotic prescribing before ureteroscopy or percutaneous nephrolithotomy. NGS will be performed on voided urine collected as routine care approximately 30 days prior to surgery. Results will be presented to ID pharmacist within 48-72 hours to help select the most appropriate antibiotics, and independently as part of routine care, surgeons will choose the antibiotic that they would use in each case, while the ID pharmacists would select their optimum choice. Pharmacists will account for site-specific antibiotic stewardship practices, allergies, medication adjustments, and C. difficile rates. Approximately 300 subjects will be randomly assigned in a 1:1 ratio to receive either NGS antibiotic recommendation or standard of care (SOC) prophylaxis prescribed treatment. All providers within the Department of Urology who perform urologic stone procedures (n=5) will also be approached in person with an information sheet. Subjects assigned to standard of care will have urine cultures sent for analysis, and the physician will choose antibiotics based on results as per usual practice. Subjects assigned to the NGS group, in addition to routine urine culture results, will have NGS urine culture results sent to an ID pharmacist, and recommendations will be shared with the physician to determine the antibiotic selection. The physician will ultimately decide the appropriate antibiotics to prescribe. Approximately 7-14 days after surgery, the research staff will conduct a telephone call to ask about any post-operative infections, complications, and any additional antibiotics that were prescribed.

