### **4.0 RESEARCH PLAN AND DATA COLLECTION**

The goal of this proposal is to evaluate if the use of NGS on preoperative antibiotic selection reduces postoperative infection rates over the standard of care. Patients scheduled to receive a transurethral procedure, such as a ureteroscopy or percutaneous nephrolithotomy (PCNL), will be approached for enrollment prior to their procedure. After informed consent has been obtained, approximately 5-10 mL of left-over urine, collected for a standard of care urine culture, will be obtained for research and sent to MicroGen Dx for NGS. Patients will be randomized to receive either standard of care culture results (only), versus NGS results and Infectious Disease (ID) Pharmacist antibiotic recommendation. The physician will utilize these results to select the best antibiotic for the case but is not required to abide by the ID pharmacist's recommendation. The standard of care group will also have a urine sample sent to MicroGen Dx, but the results will not be provided to the physician. All subjects enrolled will receive a standard of care culture as part of routine care. A chart review and/or telephone follow up will be completed approximately 7-14 days post urologic procedure to assess for complications, infections related to the procedure, and antibiotics prescribed.

The treating physicians will have control over antibiotic administration. Their determination, interaction, and ultimately patient outcome will be documented and evaluated. As a result, the treating physicians will be considered participants in this study. A waiver of documentation of informed consent for the treating physicians will be included. In addition, an information sheet will be provided to treating physicians specifically.

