5.1 Treating Physician within the Urology Clinic  
 5.2 Has a patient that is eligible to participate in this research study

## 6.0 STUDY CALENDAR

Study Visit	Visit 1	Visit 2	Visit 3	Visit 4
	Baseline	Urine collection	Transurethral Procedure (day of surgery)	Follow-up
Timeline	Day 1	Up to 90 days from V1	W/in 45 days of urine collection	Approx. 7-14 days post-surgery
Informed Consent	R			
Demographics	R			
Medical History	R	R		R
SOC Urine culture	-----SOC  -----			
Whole Urine collection	-----R  -----			
Randomization	-----R  -----			
NGS Analysis of Urine Culture	-----R  -----			
Results of NGS to Physician	-----R  -----			
Antibiotic Prophylaxis	-----SOC  -----			
Additional Antibiotics as needed	-----SOC  -----			
Provider-Participant Questionnaire/Survey	-----R  -----			
Urologic Stone Procedure			SOC	
Urologic stone collection			R*	
Chart Review and/or telephone follow up	R 	R 	R 	R 
Adverse Events	R	R	R	R

 Indicated procedures may be completed at time of baseline or visit 2, up to 90 days from enrollment  
 Indicated procedures may be repeated if SOC urine culture is not completed within 45 days of procedure  
 Patient assessments may be completed over the phone  
 \*Any extra or leftover stone(s) available will be collected and sent to MicroGen DX for analysis

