## **8.4 Randomization (research)**

A randomization list will be generated using a computer-based-random number generator [www.randomizer.org](http://www.randomizer.org). Randomization will be created 1:1, n=110 per group. Once created, individual envelopes will be created, and study staff will pull an envelope after the participant signs consent. The research staff will not be blinded to the randomization groups. The standard of care group will have urine culture results directed to treating physician. The intervention group will have NGS results sent to Infectious Disease pharmacist, [name] to provide an antibiotic recommendation. The antibiotic recommendation, along with NGS results, will then be provided to treating physician. The physician will then utilize these tools to select the best antibiotic for the case but is not required to abide by the ID pharmacist's recommendation. The standard of care group will have a urine sample sent to MicroGen Dx, but the results will not be provided to the physician.

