#### **8.8 Clinic follow up (standard of care)**

The chart will be reviewed for infections missed on phone calls.

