### **10.0 METHOD OF ANALYSIS/STATISTICS**

**Next Generation Sequencing:** Standard of care whole urine will be collected (approximately 30-50 mL) utilizing special vacutainers supplied by MicroGen Dx. Approximately 5-10mL of urine taken for culture will be sent to MicroGen Dx, a CAP-accredited and CLIA licensed clinical diagnostic lab, for analysis. MicroGen Dx will perform rapid PCR for common resistance genes prior to ureteroscopy or percutaneous nephrolithotomy. The plan will be to run target bacterial or fungi DNA on the quantitative PCR (qPCR) panel assay on the Roche LightCycler 480 II instrument and sequencing of 16S ribosomal RNA hypervariable regions V1-V2 using Ion Torrent (Ion Torrent PGM).

**Microbiome:** Sequencing reads were demultiplexed using QIIME2 software and denoised using dada2 software, using a phred score threshold of 28. Alpha diversity will be measured using the Shannon index, and a Wilcoxon test was used to determine whether the Shannon index differed between patients with stents and those without stents at the time of urine collection. Principle coordinates analysis (PCoA) of Bray-Curtis dissimilarity will be performed to visualize differences in species composition between patients with and without stents, and Linear discriminant analysis Effect Size (LEfSe) analysis was conducted to identify differentially abundant taxa between stent and non-stent groups.

**Sample size:** This will be a randomized trial of Microgen Dx versus standard of care. The primary endpoint is infection within 14 days of surgery. The primary objective of the study is to evaluate whether Microgen Dx reduces an infection rate compared to the standard of care. The null hypothesis is that infection rates within 14 days of surgery are the same between the randomization arms. The alternative hypothesis is that infection

rates within 14 days of surgery are not equal between the randomization arms. The infection rates are assumed to be 11% in the control arm and 1% in the experimental arm based on our preliminary data. A sample size of 85 per group will give 80% power to detect a 10% difference in infection rate when the two-sided Z-test with alpha=0.05 is used. Demographics and potential confounding factors will be summarized by randomization arm. A logistic regression model will be used to measure the association between the primary outcome and treatment arm with adjustment for the observed covariates.

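### The primary endpoint runs to day 14, but the only scheduled post-surgery contact may occur from about day 7 and the backup chart review has no date, so ascertainment to day 14 is not assured.

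*Combined protocol and SAP*

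**What the plan says.** The sample-size paragraph of Section 10.0 defines the outcome with a time limit: "The primary endpoint is infection within 14 days of surgery". The statistical analysis paragraph that follows restates it as a dichotomous infection outcome with no window.

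The outcome is collected in one contact, described in four places:

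- Section 1.0 (synopsis): "Approximately 7-14 days after surgery, the research staff will conduct a telephone call to ask about any post-operative infections".
- Section 4.0: "A chart review and/or telephone follow up will be completed approximately 7-14 days post urologic procedure".
- Section 6.0 (calendar), Visit 4, the only column after the day of surgery: "Approx. 7-14 days post-surgery".
- Section 8.7: "The study staff will conduct a chart review and/or telephone follow up approximately 7-14 days post urologic procedure".

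Section 8.7 also mentions a clinical follow-up visit that may come after this contact. Section 8.8, under the standard-of-care clinic heading, adds: "The chart will be reviewed for infections missed on phone calls". Neither that visit nor that review is given a day.

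On the staff involved, Section 8.4 states: "The research staff will not be blinded to the randomization groups".

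**The concern.** The contact window ends where the endpoint window ends, and it opens about a week earlier. A subject reached on day 7 can be recorded as infection-free with half of the 14 days still to run. No section requires any step to reach day 14, asks for the date of onset, or says how to classify a subject last assessed before day 14.

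The source of information can also differ between subjects. The synopsis promises a telephone call, whereas Sections 4.0 and 8.7 allow a chart review instead of one. A subject with chart review only is never asked about infections treated elsewhere.

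Two consequences follow. Late infections missed equally in both arms lower the observed rates and the power. If timing or source differed between arms, the comparison itself would be biased. Study staff make the contact, research staff know the allocation, and the documents do not say how the day within the window is chosen. Nothing shows that timing would differ by arm, but nothing prevents it.

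**Working it through.** **Inputs.** Infection rates of 11% and 1%, two-sided alpha of 0.05 and 85 per group for 80% power (Section 10.0); 110 per group randomised (Section 8.4); 250 completers, or 125 per arm (Section 8.0). The documents give no distribution of infection onset, so every missed share below is an assumption, counted after any recovery through Section 8.8.

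**The plan's own figure.** Two-proportion Z-test with unpooled variance:

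n = (1.960 + 0.842)² × (0.11 × 0.89 + 0.01 × 0.99) / 0.10² = 7.849 × 0.1078 / 0.01 = 84.6, so 85 per group.

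The figure reproduces and is not in dispute.

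**Expected infections.** 110 × (0.11 + 0.01) = 13.2; 125 × 0.12 = 15.0. Losing two or three of 13.2 is a loss of 15% to 23%.

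**Equal loss in both arms.** Both rates are multiplied by (1 − share missed). Power is the exact binomial enumeration of the uncorrected chi-squared test named in Section 10.0.

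| Share missed | Observed rates | 85 per arm | 110 per arm | 125 per arm |
|---|---|---|---|---|
| 0% | 11.0% vs 1.0% | 84.2% | 93.1% | 96.0% |
| 10% | 9.9% vs 0.9% | 79.6% | 89.9% | 93.6% |
| 20% | 8.8% vs 0.8% | 74.1% | 85.4% | 90.1% |
| 30% | 7.7% vs 0.7% | 67.8% | 79.7% | 85.1% |

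**What a given loss requires.** If contact dates and late onsets were both spread evenly and independently over days 7 to 14, half of the late infections would precede the contact. A 20% loss then needs 20% / 0.5 = 40% of infections to arise after day 7.

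**A smaller effect.** Section 3.0, Aim 1, also hypothesises a 75% reduction: 11% × 0.25 = 2.75%. At 110 per arm, power for 11% vs 2.75% is 71% with nothing missed, 66% with 10% missed and 59% with 20% missed.

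**Unequal loss, no true effect (11% in both arms).**

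- Mild case: 30% of infections arise evenly over days 7 to 14, with one arm contacted on day 12 and the other on day 14. The early arm misses 30% × 2/7 = 8.6%, so the observed rates are 11% and 10.1%. The rejection rate at 110 per arm is 5.9%, against 5.3% with no loss.
- Extreme case: all loss is in one arm. At 110 per arm the rate is 8.8% with 20% missed and 13.8% with 30% missed. At 125 per arm it goes from 5.0% to 8.9% and 14.5%.

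**The case against.** The strongest reply is that follow-up has two steps. Section 8.7 foresees a clinic visit after the study contact, and Section 8.8 exists to catch what the calls missed. In practice this may cover day 14 for many subjects. That narrows the gap without closing it: neither step has a date, neither must reach day 14, and the chart shows only charted events. A review without a cut-off or onset date could also count infections after day 14.

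A second reply is that the power loss is tolerable. At 110 per arm and 11% vs 1%, power is still 88% with 15% missed and 85% with 20%. At 150 per arm, from the roughly 300 subjects in the synopsis, it is 91.5% even with 30% missed. This stands under the planned rates. The margin depends on the 10-point difference and on more than 85 per group, and it is gone under the 75% reduction in Aim 1.

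Third, the bias is hypothetical, and the larger false-positive rates need a one-sided loss that no section suggests. This is also fair; the mild case is nearly harmless. The extreme figures only show what the present wording leaves open.

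Finally, the synopsis may simply abbreviate the method, and onset dates may be on case report forms that are not among the documents. Even so, Sections 4.0 and 8.7 still permit follow-up by chart alone.

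**Conclusion.** The concern holds, and the plan should be changed. The stated 7-to-14-day contact rule under-covers the stated 14-day endpoint, and the safeguard in Section 8.8 does not guarantee the remainder.

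The likely size is modest. Under 11% vs 1% with equal loss, the 80% power target is met or nearly met up to 30% missed at 110 or 125 per arm. At the 85 per group of the sample-size calculation, power falls just below 80% with 10% missed. Material bias would need ascertainment to differ clearly between arms, for which there is no evidence. The true loss is unknown. The documents also give no follow-up window for the pilot rate of 11%, so that figure may already contain some loss. The textual finding is firm; the size rests on assumed shares. The defect does not sink the trial, but days not followed up may be impossible to recover at analysis.

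**What to change.** - In Sections 1.0, 4.0, 6.0 and 8.7, place the outcome assessment on or after day 14 (for example days 14 to 21) for every subject in both arms, using the same scripted telephone call plus a chart review.
- Date the Section 8.8 chart review so that it covers day 14, and show it in the calendar.
- Record the date of onset and count only infections with onset on or before day 14. State in Section 10.0 how a subject last assessed before day 14 is classified, and repeat the 14-day window in the statistical analysis paragraph.
- An earlier call may stay as an additional contact, so that the alert to the medical team in Section 8.7 is not delayed.

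The cost is a wording and calendar amendment. The research call moves by up to about a week, or becomes two calls if the early one is kept. Subjects who would have had one source need staff time for the second. No new clinic visits are required.

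Dating the Section 8.8 review alone would be cheaper and would close most of the gap for charted events, but not for infections treated elsewhere. None of this blinds the classification of infections, which is a separate matter.

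### The primary outcome may be collected by chart review without a telephone call, contrary to the synopsis; infections treated elsewhere may be missed, and no single method is fixed for both arms

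*Combined protocol and SAP*

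**What the plan says.** Section 10.0 sets the endpoint: "The primary endpoint is infection within 14 days of surgery". It is analysed as a yes/no outcome by a chi-squared test.

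The places that describe how it is collected do not agree:

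- Section 8.7: "The study staff will conduct a chart review and/or telephone follow up approximately 7-14 days post urologic procedure".
- Section 4.0: "A chart review and/or telephone follow up will be completed approximately 7-14 days post urologic procedure".
- Section 6.0, calendar row: "Chart Review and/or telephone follow up".
- Section 1.0, with no alternative offered: "the research staff will conduct a telephone call to ask about any post-operative infections, complications, and any additional antibiotics that were prescribed".
- Section 8.8, which presupposes that calls were made: "The chart will be reviewed for infections missed on phone calls". It gives no date.

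On blinding, section 8.4 says: "The research staff will not be blinded to the randomization groups". No section says when a call is required, fixes one method for both arms, asks for records from outside providers, or says how a patient who is not reached is coded.

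**The concern.** Under sections 4.0, 6.0 and 8.7 a patient whose chart is reviewed and who is never called has been followed up according to protocol. Under the synopsis the same patient has not.

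The chart is a weak sole source here. Section 7.0 recruits from two local clinic settings and a Veterans hospital, and section 2.0 notes that many patients go home on the day of the procedure. Many infections would therefore appear after discharge, and some may be treated outside the enrolling system. With a yes/no endpoint and no rule for missing outcomes, an empty chart is likely to be read as no infection.

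Two things are at stake. Under-capture that is equal in the arms lowers both recorded rates and costs power. Under-capture that differs between arms produces a difference in the primary endpoint with no treatment effect behind it.

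**Working it through.** **Inputs from the document.** Infection rates 11% (control) and 1% (NGS), two-sided alpha 0.05, 85 per group for 80% power (section 10.0); 110 per group (section 8.4); about 300 randomised 1:1, so about 150 per group (section 1.0).

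**Inputs that are assumptions.** The share of infections invisible on chart-only follow-up, and the share of each arm followed by chart only. The documents give neither.

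**Step 1: the plan's own figure.** Unpooled two-proportion formula: n = (1.960 + 0.842)² × (0.11×0.89 + 0.01×0.99) / 0.10² = 84.6, so 85 per group. The stated figure reproduces and is not in dispute.

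**Step 2: expected events.** At 110 per arm: 0.11×110 = 12.1 control infections and 0.01×110 = 1.1 NGS infections. With so few events, a handful missed matters.

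**Step 3: equal under-capture.** Recorded rate = true rate × (1 − share chart-only × share invisible). With chart-only follow-up in half of each arm:

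- 30% invisible: 11% × (1 − 0.5×0.3) = 9.35%; the 1% becomes 0.85%.
- 50% invisible: 11% × (1 − 0.5×0.5) = 8.25%; the 1% becomes 0.75%.

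Power of the uncorrected chi-squared test, by exact binomial enumeration:

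| Recorded rates | 110 per arm | 150 per arm |
|---|---|---|
| 11% v 1% (full capture) | 93% | 98% |
| 9.35% v 0.85% | 88% | 96% |
| 8.25% v 0.75% | 83% | 93% |

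The pooled normal approximation is less favourable. At 110 per arm it gives 88% at full capture, 80% if 80% of infections are captured and 74% if 70% are.

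**Step 4: unequal under-capture, no true effect (11% in both arms).** Each arm's recorded rate follows the formula in step 3, with its own chart-only share. The last two columns give the chance of a significant result favouring NGS, by exact enumeration.

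| Invisible | Chart-only, NGS v control | Recorded, NGS v control | 110 per arm | 150 per arm |
|---|---|---|---|---|
| any | equal, full capture | 11% v 11% | 2.6% | 2.5% |
| 30% | 60% v 40% | 9.0% v 9.7% | 3.8% | 3.8% |
| 30% | 70% v 30% | 8.7% v 10.0% | 5.5% | 5.7% |
| 50% | 80% v 20% | 6.6% v 9.9% | 14.6% | 17.3% |

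Worked line: 0.11×(1 − 0.8×0.5) = 6.6% and 0.11×(1 − 0.2×0.5) = 9.9%. Exchanging the chart-only shares between arms gives the same probabilities in favour of standard of care.

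**The case against.** The strongest reply is that the telephone is plainly meant to be the default. The synopsis, the title of section 8.7 and the wording of section 8.8 all point that way. Section 8.8 also sits under a clinic follow-up, so the later chart review follows a patient contact at which an infection treated elsewhere could be reported and recorded. This stands in part: capture on the chart is uncertain, not nil. It does not settle the matter, because the clinic follow-up has no date, attendance is not guaranteed, and nothing requires anyone to ask about care elsewhere.

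A reader might infer three stronger things that the documents do not support:

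- That infections treated elsewhere are scored as no infection. No coding rule is written; this is only the likely default.
- That staff will choose the method by arm. Nothing in the plan says or suggests this. The text leaves it open because staff know the allocation and no method is fixed.
- That a false-positive rate of 15-17% is to be expected. It needs both 50% invisibility and an 80% v 20% split against the NGS arm. Milder inputs give 4-6%, and the direction of the split is arbitrary.

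It is also fair to say that the power loss in the equal-capture scenario is modest. Exact power at 110 per arm stays above the planned 80%.

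**Conclusion.** The sections conflict on how the primary outcome is collected, and the operative ones permit follow-up that can miss infections treated outside the enrolling system. Differential ascertainment is possible but not planned.

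The size depends wholly on assumed values. A false benefit for NGS has a chance of about 4-6% under moderate assumptions and 15-17% in the worst case considered, against 2.5%. Equal under-capture in the scenario shown lowers exact power at 110 per arm from 93% to 83-88%. The plan should be changed because the remedy is cheap and concerns the primary endpoint; confidence in the size of the effect is no more than medium.

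**What to change.** In sections 4.0, 6.0 and 8.7, replace the *and/or* wording with: chart review and a scripted telephone call, including a question on care received elsewhere, for every randomised patient in both arms. Align sections 1.0 and 8.8 with this.

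Record for each patient which source supplied the outcome. Treat a patient who is not reached and has no charted post-operative contact as outcome missing, and report these patients by arm. Because such patients may be mostly well, leaving them out could raise the recorded rates. Section 10.0 should therefore add a sensitivity analysis that counts them first as infection-free and then as infected.

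The cost is protocol wording, one call script and some staff time for repeat call attempts; the synopsis already plans the calls. The change does not remove the separate issue of unblinded assessment, since the staff making the calls would still know the arm.

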**Statistical analysis:** Our primary outcome is infection after surgery as a dichotomous outcome. We will utilize a chi-squared analysis to determine the difference between intervention and control groups. We will assess demographics between groups using chi-squared for dichotomous variables and Student's t-test for continuous variables. Additionally, we will investigate the utilization of antibiotic in a mixed-model regarding a number of antibiotics and antibiotic class utilization.

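### The plan does not settle whether the primary endpoint is every infection to day 14 or only procedure-related infections, and unblinded staff have no rule for telling them apart

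*Combined protocol and SAP*

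**What the plan says.** The statements about the outcome fall into two groups.

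Without a limit by cause:
- Section 10.0, sample size: "The primary endpoint is infection within 14 days of surgery". The null and alternative hypotheses use the same wording.
- Section 10.0, statistical analysis: "Our primary outcome is infection after surgery as a dichotomous outcome".
- Section 1.0, synopsis: the call after surgery is "to ask about any post-operative infections, complications, and any additional antibiotics that were prescribed".
- Section 8.8: "The chart will be reviewed for infections missed on phone calls".

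With a limit by cause:
- Section 4.0: the chart review or telephone follow-up is "to assess for complications, infections related to the procedure, and antibiotics prescribed".
- Section 8.7 repeats this for the follow-up contact: "complications, infections related to the procedure, and antibiotics prescribed".

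On who does the work, section 8.7 says "The study staff will conduct a chart review and/or telephone follow up approximately 7-14 days post urologic procedure", and section 8.4 says "The research staff will not be blinded to the randomization groups". The documents do not define infection or relatedness, do not say who judges relatedness, and do not provide for blinded adjudication.

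**The concern.** Section 8.7 is the text that the person making the call is most likely to follow. Someone working from it could leave out an infection that someone working from the synopsis would count, so the same patient could be an event or a non-event depending on the section used.

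The difference matters because relatedness is a judgement and the staff making it know the arm. Randomisation balances the patients. It does not protect against a subjective exclusion applied afterwards, when the outcome is classified. If infections in one arm are more readily called unrelated, the comparison is biased even when the treatment does nothing. Defining infection well would not cure this, because a clearly diagnosed infection could still be set aside on cause.

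**Working it through.** **1. The plan's own figure.** Inputs from section 10.0: 11% versus 1%, two-sided alpha 0.05, 80% power. With the unpooled Z formula, n = (1.960 + 0.842)² × (0.11×0.89 + 0.01×0.99) / 0.10² = 7.85 × 0.1078 / 0.01 = 84.6, rounded up to 85 per group. The stated 85 reproduces. The documents do not say whether the 11% and 1% count all infections or only procedure-related ones.

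**2. Size per arm.** Section 8.4 gives 110 per group. The synopsis gives about 300 subjects, so 150 per arm. The range used below is 110-150.

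**3. Test.** This is the chi-squared test of section 10.0. With x_C and x_N events in n per arm and p̄ = (x_C + x_N)/(2n), z = (x_C/n − x_N/n) / √(2p̄(1−p̄)/n). A result favours NGS when z > 1.96. Its probability is the sum of the products of the two binomial probabilities over all such pairs (exact enumeration).

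**4. Relatedness calls that differ by arm, with no true effect.** These inputs are assumptions and none is in the documents: the true rate is 11% in both arms, a share u of infections is debatable, and staff set aside 25% of the debatable ones in control and 75% in the NGS arm.
- No filtering: the chance of a significant result favouring NGS is 2.6% at 110 per arm and 2.5% at 150.
- u = 30%: recorded control rate 0.11 × (1 − 0.30×0.25) = 10.2%; recorded NGS rate 0.11 × (1 − 0.30×0.75) = 8.5%; risk ratio 0.775/0.925 = 0.84. The chance is 6.4% at 110 and 7.0% at 150.
- u = 50%: recorded rates 9.6% and 6.9%; risk ratio 0.625/0.875 = 0.71. The chance is 11.5% at 110 and 13.2% at 150.

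The direction is also assumed. With the two arms' shares swapped, the same figures apply to a false result against NGS.

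**5. Few events.** At 11%, 110 control patients give about 12 infections. Against 12/110, an NGS count of 4/110 gives p = 0.038 and 5/110 gives p = 0.077, so one reclassified event can cross the 5% line.

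**6. The cost of counting everything.** Suppose 11% and 1% are procedure-related rates and truly unrelated infections add the same number of points to each arm. Exact power at 110 per arm is:
- nothing added (11% vs 1%): 93%
- 1 point (12% vs 2%): about 88%
- 3 points (14% vs 4%): about 77%
- 5 points (16% vs 6%): about 68%

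**The case against.** The strongest reply is that this is loose wording and not a procedure. The phrase in sections 4.0 and 8.7 may be shorthand for postoperative infection, which is what Aim 1 speaks of. No section tells staff to judge causation, to leave an infection off the form, or to analyse only related ones. The other statements point the other way, and further sources would leave a trace: sections 4.0 and 8.7 also collect antibiotics prescribed, and the study calendar lists adverse events and chart review or telephone follow-up at every visit.

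Much of that stands. A reader might infer that follow-up captures only related infections, or that the rest are never recorded and cannot be recovered. The synopsis and section 8.8 contradict the first, and nothing supports the second. It would also go too far to say that the endpoint analysed is known to differ from the one stated.

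A reader might also infer a serious loss of power. If 30% of infections were set aside equally in both arms (7.7% versus 0.7%), exact power at 85 per arm would fall from 84% to 68%. But section 8.4 plans 110 per group, where the same assumption leaves about 80%, so the 68% does not describe the planned trial. The fragility in step 5 of the working belongs to any rare binary endpoint and is not evidence of filtering.

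The reply does not remove the conflict. The synopsis is one side of it and does not resolve it. Section 8.8 looks for infections that the calls missed; one that was heard about and judged unrelated was not missed. An event that appears as a complication or an antibiotic course still needs a rule saying whether it is a primary event.

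**Conclusion.** The point holds as an inconsistency in the primary endpoint that should be corrected. Four places state or collect infection without regard to cause (synopsis, section 8.8, and both statements in section 10.0), and two restrict it to procedure-related infection (4.0 and 8.7). With unblinded staff and no relatedness rule, following the restrictive text would put an arm-aware judgement on the primary outcome.

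Whether bias would follow, and how much, cannot be established from the documents. The rise to 6.4-7.0% shows what a threefold difference between arms in setting aside debatable infections would do if 30% were debatable. It is not an estimate for this trial.

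**What to change.** In sections 4.0 and 8.7, replace the causal restriction with: *all infections with onset within 14 days of surgery, whatever the judged cause*. Use that count for the primary test, as section 10.0 already states. Record relatedness as a separate field for a secondary analysis only, classified without knowledge of arm where existing staff allow.

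The cost is two wording edits and one case-report-form field, with no effect on patient care. The statistical price is the dilution in step 6 of the working: exact power at 110 per arm falls from 93% to about 88-77% if unrelated infections add 1-3 points to each arm. The sponsor should state which kind of infection the 11% and 1% represent, so that this price is known in advance. Recording every infection keeps both analyses possible.

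The edit does not by itself supply a case definition of infection, or remove unblinded judgement about whether an infection occurred.
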